4.4.2 Prohibited Therapy

Use of the following therapies (excluding protocol-specified treatments) is prohibited during the study:

- Any anti-cancer therapy, approved or investigational, other than intrathecal CNS prophylaxis
- Hormonal therapy other than contraceptives, stable hormone replacement therapy, or megestrol acetate
- Biologic agents other than hematopoietic growth factors (as described in Section 4.3.2.7)
- Immunostimulatory agents, including, but not limited to, IFN- α , IFN- γ , or IL-2
 - Immunostimulatory agents, in combination with atezolizumab, could potentially increase the risk for autoimmune conditions. Patients should not receive other immunostimulatory agents for 10 weeks after the last dose of atezolizumab.
- Vaccines, as outlined below:
 - Any live, attenuated vaccine (e.g., FluMist[®]) is prohibited while the patient is receiving atezolizumab and for a period of five months after discontinuation of atezolizumab. Inactivated influenza vaccines are allowed only during flu season.
 - Vaccination with live vaccines is not recommended during treatment with obinutuzumab and until B-cell recovery.

4.5 STUDY ASSESSMENTS

See [Appendix 1](#) and [Appendix 2](#) for the schedules of assessments performed during the study.

4.5.1 Informed Consent Forms, Screening Log, and Patient Screening

Written informed consent for participation in the study must be obtained before performing any study-related procedures. Informed Consent Forms for enrolled patients and for patients who are not subsequently enrolled will be maintained at the study site.

All screening evaluations must be completed and reviewed to confirm that patients meet all eligibility criteria before enrollment. The investigator will maintain a screening log to record details of all patients screened and to confirm eligibility or record reasons for screening failure, as applicable.

Results of standard-of-care tests or examinations performed prior to obtaining informed consent, and within the defined window, may be used as screening and baseline assessments (see [Appendix 1](#) and [Appendix 2](#)); such tests do not need to be repeated for screening purposes (e.g., screening tumor assessment).

Study treatment should be initiated within 28 days after the Informed Consent Form has been signed.

Patients who fail screening based on longer waiting time for certain results or due to study administrative reasons (e.g., a dose cohort or enrollment hold) can be rescreened at a later date, and only once, if they were deemed eligible before the screen failure. The decision to rescreen individual patients will be made jointly by the Roche Medical Monitor and the investigator and any other person the investigator or Medical Monitor considers necessary to assist with this decision. Any such decision and the reasons for it will be clearly documented. Any out of window assessments need to be repeated and undergo a complete review by the Roche Medical Monitor.

4.5.2 Medical History and Demographic Data

Medical history includes clinically significant diseases, surgeries, reproductive status, smoking history, and alcohol and drug abuse. In addition, all medications (e.g., prescription drugs, over-the-counter drugs, herbal or homeopathic remedies, nutritional supplements) used by the patient within seven days prior to the screening period will be recorded.

Demographic data will include age, sex, and self-reported race/ethnicity.

The following clinical parameters relative to disease history, diagnosis, and prognostic indices will be recorded at screening:

- Date of initial diagnosis
- ECOG Performance Status (see [Appendix 6](#))
- B symptoms (unexplained fever $>38^{\circ}\text{C}$, night sweats, and unexplained weight loss $>10\%$ of body weight over 6 months)

- Ann Arbor staging (see [Appendix 7](#))
- For patients with FL: Follicular Lymphoma International Prognostic Index (FLIPI) and Follicular Lymphoma International Prognostic Index 2 (FLIPI2) (see [Appendix 8](#))
- For patients with DLBCL: The IPI (see [Appendix 8](#))
- Prior anti-lymphoma treatment, as well as response to prior treatment, date of disease progression in relation to start date of prior treatment, and date of last dose of prior treatment

4.5.3 Physical Examinations

A complete physical examination should be performed at screening and should include an evaluation of the head, eyes, ears, nose, and throat and the cardiovascular, dermatological, musculoskeletal, respiratory, GI, genitourinary, and neurological systems. Any abnormality identified at baseline should be recorded on the General Medical History and Baseline Conditions eCRF.

As part of tumor assessment, the physical examination should include evaluation for the presence of enlarged nodes, palpable hepatomegaly, and splenomegaly. This information will be recorded on the appropriate tumor assessment eCRF.

At subsequent visits (or as clinically indicated), targeted (limited, symptom-directed) physical examinations should be performed. Targeted physical examinations should be limited to systems of primary relevance (e.g., cardiovascular and respiratory systems), systems associated with symptoms (newly emergent or monitored from baseline), and areas associated with tumor assessment (lymph nodes, liver, spleen, and any other areas identified at baseline) (see Section [4.5.5](#)).

Changes from baseline abnormalities should be recorded in patient notes. New or worsened clinically significant abnormalities should be recorded as adverse events on the Adverse Event eCRF.

4.5.4 Vital Signs

Vital signs will include measurements of respiratory rate, pulse rate, body temperature, and systolic and diastolic blood pressures while the patient is in a seated position. Vital sign measurements will be performed as outlined in the schedules of assessments (see [Appendix 1](#) and [Appendix 2](#)), but the associated data, other than the data collected at screening, do not need to be recorded on the eCRF (except in the case of an adverse event as presented in Section [5.3.5.6](#)).

4.5.5 Tumor and Response Evaluations

All evaluable or measurable disease must be documented at screening and re-assessed at each subsequent tumor evaluation. Response will be assessed by the investigator on the basis of PET and CT scans using the Lugano 2014 criteria (see [Appendix 5](#)). In this study, the Lugano 2014 criteria for a PET-CT-based CR and PR have been modified, as outlined below:

- A designation of PET-CT-based CR requires normal bone marrow by morphology for patients with bone marrow involvement at baseline. If indeterminate by morphology, immunohistochemistry should be negative.
- A designation of PET-CT-based PR requires that CT-based response criteria for a CR or PR be met in addition to the PET-CT-based response criteria for a PR.

4.5.6 Radiographic Assessments

The PET scans should include skull-base to mid-thigh. Full body PET scans should be performed when clinically appropriate.

The CT scans with oral and IV contrast should include chest, abdomen, and pelvic scans. The CT scans of the neck should be included if clinically indicated (i.e., if evidence of disease upon physical examination) and must be repeated throughout the study if there is disease involvement at baseline.

The PET-CT scans and diagnostic CT scans should be acquired according to a standardized imaging manual, which will be provided to all sites.

If contrast is medically contraindicated (e.g., patients with contrast allergy or impaired renal clearance), MRI scans of the chest, abdomen, and pelvis (and neck, if clinically indicated) and a non-contrast CT scan of the chest may be performed. If MRI scans cannot be obtained, CT scans without contrast are permitted as long as these allow consistent and precise measurement of the targeted lesions during the study treatment period.

The same radiographic assessment modality must be used for all response evaluations to ensure consistency across different timepoints (including unscheduled assessments).

A full tumor assessment, including radiographic assessment, must be performed any time disease progression or relapse is suspected. Additional details regarding imaging procedures will be provided in the Imaging Manual.

4.5.6.1 Bone Marrow Assessments

Bone marrow examinations are required at screening for staging purposes in all patients and should be performed within approximately 3 months prior to Day 1 of Cycle 1.

If bone marrow infiltration is present at screening, a bone marrow biopsy is required at the EOI response assessment for all patients who may have achieved a CR. In patients with a PR at EOI, a subsequent bone marrow examination may be required to confirm a CR at a later timepoint.

Any additional (unscheduled) bone marrow examinations performed during the study will be at the discretion of the investigator.

4.5.7 Laboratory, Biomarker, and Other Biological Samples

Local Laboratory Assessments

Samples for the following laboratory tests will be analyzed at the study site's local laboratory for analysis:

- Hematology: hemoglobin, hematocrit, platelet count, RBC count, WBC count, percent or absolute WBC differential count (neutrophils, eosinophils, basophils, monocytes, lymphocytes, and other cells)
- Chemistry panel (serum or plasma): sodium, potassium, glucose, BUN or urea, creatinine, calculated creatinine clearance, calcium, total bilirubin, direct bilirubin, total protein, albumin, ALT, AST, alkaline phosphatase (ALP), LDH, uric acid, glycosylated hemoglobin (HbA_{1c}), amylase, and lipase.

HbA_{1c} will be measured only at screening and can be obtained in a non-fasting state.

- Thyroid-stimulating hormone, triiodothyronine, thyroxine (T4)
- β 2 microglobulin
- Coagulation: INR, aPTT (or PTT), and PT
- Pregnancy test

All women of childbearing potential will have a serum pregnancy test at screening (within 7 days of Day 1 of Cycle 1). In addition, urine pregnancy testing is required monthly during induction. If a urine pregnancy test is positive, it must be confirmed by a serum pregnancy test.

- Viral serology
 - Hepatitis B testing includes HBsAg and total HBcAb.
 - Hepatitis C testing includes HCV antibody.
- Quantitative immunoglobulins: IgA, IgG, and IgM

Central Laboratory Assessments

The following samples will be sent to one or several Sponsor-designated central laboratories or to the Sponsor for analysis:

- Serum samples for obinutuzumab PK analysis using a validated assay
- Serum samples for rituximab PK analysis using a validated assay
- Serum samples for atezolizumab PK analysis using a validated assay

- Serum and plasma samples for polatuzumab vedotin PK analysis using a validated assay
- Serum samples for assessment of HAAs to obinutuzumab using a validated assay
- Serum samples for assessment of HACAs to rituximab using a validated assay
- Serum samples for assessment of ATAs to atezolizumab using a validated assay
- Serum samples for assessment of ATAs to polatuzumab vedotin using a validated assay
- Tumor tissue samples and the corresponding pathology report for retrospective central confirmation of the diagnosis of FL or DLBCL, and for exploratory research on candidate biomarkers (see [Table 10](#)).

The specimen must contain adequate evaluable tumor cells ($\geq 20\%$ for excisional biopsy and $\geq 50\%$ for core biopsy).

Formalin-fixed paraffin-embedded tissue blocks are preferred over slides. Tissue blocks that are not formalin fixed will be accepted in countries that use a fixative other than paraformaldehyde, but information on the type of fixative should be included. If a tissue block is not available, 15–20 serial, freshly cut, unstained slides accompanied by a punch biopsy may be sent. A tumor block or punch biopsy is required for construction of a tissue microarray. If less than 15–20 unstained serial slides are available, the study site should consult the Sponsor (or delegate) regarding the acceptability of a fewer number of slides.

If archival tissue is unavailable or unacceptable according to the above criteria, a pretreatment core-needle, excisional, or incisional tumor biopsy is required. Cytological or fine-needle aspiration samples are not acceptable.

If the patient received anti-lymphoma treatment between the time of the most recent available biopsy and initiation of study treatment, or if the available biopsy was performed more than 6 months prior to Day 1 of Cycle 1 (initiation of study treatment) for patients with DLBCL or more than 12 months prior to Day 1 of Cycle 1 for patients with FL, a core-needle biopsy is strongly recommended.

The sample should be shipped according to instructions provided in the laboratory manual. The remainder of the tissue blocks will be returned to the local pathology laboratory, according to country-specific procedures.

Analysis methods will be detailed in the Biomarker Analysis Plan.

- Tumor biopsy samples obtained prior to the start of Cycle 2 and at the time of progression (unless no adequate tumor site is accessible) for exploratory research on candidate biomarkers ([Table 10](#))
- Serum samples for exploratory research on candidate biomarkers (see [Table 10](#))
- Whole blood samples for exploratory research on candidate biomarkers (see [Table 10](#))
- Whole blood samples for isolation of peripheral blood mononuclear cells for exploratory research on candidate biomarkers (see [Table 10](#))

Exploratory biomarker research may include, but will not be limited to, the biomarkers listed in [Table 10](#).

Table 10 Proposed Non-Inherited Biomarkers for Exploratory Research

Sample Type	Timing	Proposed Non-Inherited Biomarkers
Archival or fresh tumor tissue	Prior to study (archival) or baseline (fresh)	
 For patients with DLBCL only: DLBCL cell-of-origin subtype (ABC vs. GCB), MYC, BCL2, Epstein-Barr virus status CD79b Lymphoma-related genetic changes (DNA) and gene expression (mRNA) PD-L1, HLA-1 CD8 and other biomarkers of T-cell subpopulations Biomarkers of other immune cells (such as macrophages)
Tumor tissue biopsy	Prior to the start of Cycle 2 and at the time of progression (unless no adequate tumor site is accessible)	
 PD-L1 CD8 and other biomarkers of T-cell subpopulations and other immune cells
Plasma	Baseline	
 Soluble PD-L1
Plasma	Baseline and subsequent timepoints during treatment	
 Cytokines characteristic of T-cell activation (e.g., IL-18, IFN-γ)
PBMCs isolated from whole blood	Baseline and subsequent timepoints during treatment	
 T-cell receptor repertoire
Whole blood	Baseline and subsequent timepoints during and after treatment	
 Lymphocyte immunophenotyping, including B-cell counts (CD19), T-cell counts (CD3, CD4, and CD8), and NK cell counts (CD16 and CD56)

ABC=activated B cell-like; DBCL=diffuse large B-cell lymphoma; GCB=germinal-center B cell-like; HLA=human lymphocyte antigen; IFN- γ =interferon gamma; IL=interleukin; NK=natural killer; PBMC=peripheral blood mononuclear cell.

Note: Exploratory biomarker research may include, but will not be limited to, the biomarkers listed in this table.

Samples collected for PK and immunogenicity analyses may be used for assay development purposes and additional safety and immunogenicity assessments, as appropriate.

Biological samples will be destroyed when the final Clinical Study Report has been completed, unless the patient gives specific consent for the leftover samples to be stored for optional exploratory research (see Section 4.5.9).

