The highest dose at which fewer than 2 of 6 patients DLT-evaluable patients (i.e., <33%) experience a DLT was declared the RP2D for polatuzumab vedotin that will be used in the expansion phase.

On the basis of a review of real-time safety data and available preliminary PK data, dose escalation may be halted or modified by the Sponsor as deemed appropriate.

Relevant demographic, adverse event, laboratory, and PK (if available) data will be reviewed prior to dose-escalation decisions, by the Medical Monitor in consultation with the Principal Investigator and participating investigators.

Although the DLT assessment window is defined as Cycles 1 and 2, cumulative toxicities occurring beyond Cycle 2 may be considered when determining the RP2D.

Patients enrolled in the dose-escalation phase that achieved a CR, a PR, or stable disease at EOI received maintenance treatment with G+Atezo.

As of 1 March 2018, patients with RR FL eligible to or already receiving maintenance treatment will continue to receive obinutuzumab maintenance treatment, as outlined in [Table 2](#). Maintenance treatment should start 8 weeks (\pm 1 week) after Day 1 of Cycle 6 and will continue until disease progression or unacceptable toxicity for up to 24 months.

Table 2 Maintenance Treatment for the G+Atezo+ Pola Treatment Group

Patients	Treatment
Patients with FL	Maintenance treatment consisting of the following, administered for 24 months ^a (from Month 1–Month 24): Obinutuzumab 1000 mg IV on Day 1 of every other month (i.e., every 2 months), starting with Month 1

FL=follicular lymphoma; IV=intravenous.

^a 1 month=28 days.

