3.1.3.1 Treatment Regimens and Safety Run-In Rules

Patients with DLBCL enrolled in the safety run-in phase and the expansion phase were planned to receive induction treatment with R + Atezo + Pola for a total of 6 cycles.

Patients achieving a CR or PR at EOI were eligible to receive consolidation treatment with R + Atezo.

[figure not shown]
As of 1 March 2018, patients with RR DLBCL will continue to be treated as outlined in [Table 4](#). As of Protocol BO29561, Version 7, patients who have completed or prematurely discontinued induction treatment will proceed to the safety follow-up without consolidation treatment.

Table 4 Induction Treatment for Patients with Diffuse Large B-cell Lymphoma

Cycle	R + Atezo + Pola (21-Day Cycles) Treatment Group
1–6	Rituximab 375 mg/m ² IV on Day 1 Polatuzumab vedotin 1.8 mg/kg IV on Day 1

IV=intravenous.

Figure 1 Study Schema

C=cycle; CR=complete response; D=day; D1C6=Day 1 of Cycle 6; EOI=end of induction; FL=follicular lymphoma; G=obinutuzumab; M=month; Pola=polatuzumab vedotin; PR=partial response; R=rituximab; q2m=every 2 months; SD=stable disease.

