3.1.4 Internal Monitoring Committee

An IMC will monitor patient safety throughout the study. The IMC will include Sponsor representatives from Clinical Science, Drug Safety, Biostatistics, and Statistical Programming and Analysis. In addition to the ongoing assessment of the incidence and nature of adverse events (particularly Grade ≥ 3 events), SAEs, deaths, and laboratory abnormalities performed by the investigator and the Medical Monitor, the IMC will review data supporting the determination of the RP2D and then, at regular intervals during the expansion phase. At the time of each review, the IMC will make appropriate

recommendations (e.g., the study should continue as planned, additional analyses should be performed, enrollment should be held pending further safety evaluations). Decisions will be made in consideration of the totality of the available data. Ad hoc meetings may be called in addition to scheduled meetings, as necessary, to provide recommendations on management of any potential new safety signals. *Following protocol amendment Version 7, patients are no longer receiving atezolizumab or polatuzumab. Therefore, regular IMC assessments will no longer take place. Ad hoc meetings to review safety data maybe called at the discretion of the Medical Monitor in case of newly identified safety signals.* Specific operational details such as the committee's composition, frequency and timing of meetings, members' roles and responsibilities, and data to be reviewed will be detailed in an IMC charter.

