4.6.2 Study Treatment Discontinuation

Study treatment should be permanently discontinued in patients who experience any of the following:

- Anaphylaxis, acute respiratory distress, or Grade 4 IRR
If a Grade 3 IRR is recurrent during the second and subsequent cycles, study treatment may be discontinued at the discretion of the investigator, following an individual benefit-risk assessment.
- Life-threatening adverse event
- Grade ≥ 3 non-immune-related adverse event that is considered to be related to study treatment and does not resolve to Grade ≤ 2 within 21 days
- Non-immune-related adverse event that is considered to be treatment related and requires study treatment to be withheld for >21 days
- Grade ≥ 3 immune-related adverse event that is considered to be related to atezolizumab or requires atezolizumab to be withheld for >42 days, unless approved by the Medical Monitor
- Any adverse event that meets criteria for permanent discontinuation per guidelines provided in Section 5.1

- Disease progression

Because of the potential for tumor flares with immunotherapies, resulting in early apparent radiographic progression (pseudoprogression/tumor immune infiltration), including the appearance of new lesions followed by delayed response (Wolchok et al. 2009), patients whose CT scans meet the criteria for disease progression may continue to receive study treatment at the discretion of the investigator and following discussion with the Medical Monitor, if certain criteria are met (see Section 4.1 for details). Cases of delayed pseudoprogression have also been described in patients with solid tumors treated with immunotherapies. In case of CT- findings suggestive for pseudoprogression in patients with persistent clinical benefit, the investigator should contact the Medical Monitor to discuss further patient management. Patients who continue to receive study treatment should have a CT scan repeated 4–8 weeks later.

- Pregnancy

In case of toxicity solely attributable to one drug of the combination requiring discontinuation, the other study drugs may be continued for patients experiencing clinical benefit as determined by the investigator after discussion with the Medical Monitor.

The primary reason for study treatment discontinuation should be documented on the appropriate eCRF.

Patients who discontinue study treatment will not be replaced, except as outlined below:

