- ⁱ As part of tumor assessment, the physical examination should include evaluation for the presence of enlarged nodes, palpable hepatomegaly, and splenomegaly. This information will be recorded on the appropriate tumor assessment eCRF.
- ^j Includes systems of primary relevance (e.g., cardiovascular and respiratory systems), systems associated with symptoms (newly emergent or monitored from baseline), and areas associated with tumor assessment (lymph nodes, liver, spleen, and any other areas identified at baseline). Record new or worsened clinically significant abnormalities on the Adverse Event eCRF.
- ^k Unexplained fever $>38^{\circ}\text{C}$, night sweats, and unexplained weight loss $>10\%$ of body weight over 6 months.
- ^l Includes hemoglobin, hematocrit, platelet count, RBC count, WBC count, and percent or absolute WBC differential count (neutrophils, eosinophils, basophils, monocytes, lymphocytes, other cells).
- ^m Screening laboratory assessments may be used for Day 1 of Cycle 1 if performed within 72 hours prior to Day 1 of Cycle 1.
- ⁿ Perform hematology and chemistry tests within 72 hours prior to Day 1 of each cycle during induction or every 2 months during maintenance, and within 24 hours prior to other timepoints during induction treatment. Samples for exploratory biomarker research should be collected at the same time as hematology and chemistry samples.
- ^o Includes sodium, potassium, glucose, BUN or urea, creatinine, calculated creatinine clearance, calcium, total bilirubin, direct bilirubin, total protein, albumin, ALT, AST, alkaline phosphatase, glycosylated hemoglobin (HbA_{1c}), amylase, lipase, LDH, and uric acid. HbA_{1c} will be measured only at screening and can be obtained in a non-fasting state.
- ^p All women of childbearing potential will have a serum pregnancy test at screening, within 7 days prior to Day 1 of Cycle 1. Urine pregnancy tests will be performed at specified subsequent visits. If a urine pregnancy test is positive, it must be confirmed by a serum pregnancy test.

Appendix 1

Schedule of Assessments for Patients with Follicular Lymphoma (cont.)

- q Includes hepatitis B surface antigen, total hepatitis B core antibody, and hepatitis C virus antibody.
- r Perform at the same time as tumor assessments at 12, 18, and 24 months after initiation of induction treatment.
- s See [Appendix 3](#) for detailed schedule.

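### No pregnancy test is scheduled for women of childbearing potential with FL during obinutuzumab maintenance, although pregnancy is a mandatory reason to stop treatment

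*Combined protocol and SAP*

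**What the plan says.** Section 4.5.7 requires a serum test at screening for women of childbearing potential and continues: "In addition, urine pregnancy testing is required monthly during induction". No frequency is given for maintenance.

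In Appendix 1 the pregnancy test row is marked at screening, Day 1 of Cycles 2–6, EOI and one visit after maintenance. Both maintenance cells are empty. Footnote p says "Urine pregnancy tests will be performed at specified subsequent visits", so it adds no visit beyond those marked. The EOI mark carries footnote g, which limits that test to patients not going on to maintenance.

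Table 2 (Section 3.1.2.1.2) gives the maintenance regimen: "Obinutuzumab 1000 mg IV on Day 1 of every other month (i.e., every 2 months), starting with Month 1", for up to 24 months, with "1 month=28 days". Blood tests do continue at these visits. Appendix 1, footnote n: "Perform hematology and chemistry tests within 72 hours prior to Day 1 of each cycle during induction or every 2 months during maintenance".

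Section 4.6.2 states: "Study treatment should be permanently discontinued in patients who experience any of the following". Pregnancy is on that list. Section 5.4.3.1 tells the investigator to stop treatment and counsel the patient, and relies on the patient to report a pregnancy. Section 4.1.1 requires contraception with a failure rate below 1% per year during treatment and for at least 18 months after obinutuzumab. The corresponding periods are 12 months for polatuzumab vedotin and rituximab, and 5 months for atezolizumab.

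**The concern.** A rule to stop treatment for pregnancy works only if the pregnancy is recognised. During induction the protocol does not rely on contraception alone; it adds regular testing to the same contraception requirement. During maintenance the testing stops while dosing goes on, and the drug still being given is the one with the longest post-treatment contraception period for women. Hematology and chemistry resume every 2 months in maintenance, but the pregnancy test does not. Each further 56 days before a pregnancy is recognised means one more infusion.

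The gap matters more under the current version. Section 3.1.4 says that, following Version 7, "patients are no longer receiving atezolizumab or polatuzumab". For DLBCL, Section 3.1.3.1 says that "patients who have completed or prematurely discontinued induction treatment will proceed to the safety follow-up without consolidation treatment". Taken together, these suggest that anyone still being dosed is an FL patient in obinutuzumab maintenance. On that reading, no on-treatment pregnancy test in the schedule applies to her.

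**Working it through.** The documents state no test-to-test interval, so there is no figure of theirs to reproduce. The interval follows from the schedule.

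**Inputs**
- Induction cycles of 21 days, with a test marked on Day 1 of Cycles 2–6 (Appendix 1). The last induction test is taken to be on Cycle 6 Day 1.
- Assessments precede dosing on treatment days (Appendix 1, notes), so the Cycle 6 Day 1 dose follows that day's test.
- No EOI test for a patient entering maintenance (footnote g).
- Maintenance starts 8 weeks ± 1 week after Cycle 6 Day 1; a month is 28 days; doses fall in Months 1, 3, …, 23 (Table 2).
- EOM visit 35 days after the last dose (Appendix 1).

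**Nominal interval for a patient who completes maintenance**
1. Cycle 6 Day 1 = 1 + 5 × 21 = day 106.
2. First maintenance dose = 106 + 56 = day 162.
3. Maintenance doses: 12. First to last = 22 × 28 = 616 days, so the last dose is on day 778.
4. EOM = 778 + 35 = day 813.
5. Test to test = 813 − 106 = 56 + 616 + 35 = **707 days**.
6. Doses after the Cycle 6 Day 1 test = 1 + 12 = **13**.

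**Variation around 707**
- Start window of ± 7 days: 700 to 714. With the last dose a further week late: 721.
- One 42-day hold, the longest Table 15 allows: 707 + 42 = 749.
- The column alignment of Appendix 1 is uncertain in the text available to me. If the last mark belongs to the 90-day visit and not to EOM: 56 + 616 + 90 = 762. Neither alignment puts a mark in maintenance.

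**Patient already in maintenance, r doses left**

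Next dose to EOM = 35 + 56(r − 1) days: 651 for r = 12, 315 for r = 6, 35 for r = 1.

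**Scale of the risk**

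If contraception performs exactly at the 1% per year limit, expected pregnancies over 707 days are 0.01 × 707/365 = 0.019 per woman. For three women the figure is 0.058. Three is the number of remaining patients given in the summary of changes for a PK sample; that all three are women of childbearing potential on treatment is an assumption. These figures count all pregnancies. Those that go unrecognised long enough for another infusion, which are the ones testing would address, would be fewer.

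**With a test before each maintenance dose**

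Gaps are 56 days (Cycle 6 to first dose), 56 days (between doses) and 35 days (last dose to EOM). The longest nominal gap is 56 days. If the final mark is the 90-day visit, the last gap is 90 days, but no dose falls in it.

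**The case against.** The strongest reply is that this is a design choice. Text and table agree, and nothing in the protocol requires a test in maintenance. Pregnancy is handled by contraception, immediate self-report and mandatory discontinuation. Monthly testing may also have been aimed at polatuzumab vedotin, whose expected reproductive toxicity Section 5.1.4.2 describes and which is not given in maintenance. It stands that this is an omission and not a contradiction. It does not settle the matter: the same contraception rule applies in induction, where testing was still added, and the protocol sets the longest contraception period for obinutuzumab.

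A reader might also infer that nothing scheduled in maintenance could reveal a pregnancy. The documents do not support that. Appendix 1 schedules CT at 12, 18 and 24 months after induction starts, and targeted physical examinations after induction. Section 5.3.2 has patients asked about new health problems. A pregnancy might come to light at any of these, but only by chance; none is a pregnancy test.

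**Conclusion.** The point holds as a minor gap in the schedule. No pregnancy test is planned during obinutuzumab maintenance, and for a patient who completes it the nominal interval between tests is about 707 days, with 13 doses after the last test.

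Two stronger readings should be avoided:
- **That 707 days is a maximum, or the exposure still ahead of current patients.** Windows, holds or the 90-day reading lengthen it to between 714 and 762 days. Enrollment stopped on 1 March 2018, so much of the interval may already have passed. What remains depends on r, which the documents do not give.
- **That Section 3.1.4 states obinutuzumab is the only treatment still running.** It does not name obinutuzumab. The conclusion is an inference from Sections 3.1.4 and 3.1.3.1 together, and the current text still carries the obinutuzumab–polatuzumab and rituximab–polatuzumab induction tables.

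Thirteen FL patients had been enrolled by 1 March 2018. How many are women of childbearing potential is not stated and may be zero. No endpoint or analysis is affected. The absence of a scheduled test and the date arithmetic are firm; the number of women concerned is unknown.

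**What to change.** In Appendix 1, enter the urine pregnancy test already described in footnote p in the 'Every 2 months' maintenance column, before dosing, for women of childbearing potential. In Section 4.5.7, change the frequency to *monthly during induction and before each maintenance dose*.

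This is one table cell and one phrase. The test falls at dosing visits that already have pre-dose bloods, so it adds no visit and no invasive procedure. On the assumption that three women of childbearing potential remain on treatment, the total is 3r tests: 3 with one dose left each, 18 with six, and 36 with all twelve. If the extension study allowed by Section 4.3.4 reuses this schedule, the same entry should be carried over.
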